2.5. End of Study, End of Treatment, End of Treatment Visit, Follow-up Period

End of Study (EOS) is defined as either the date of the last visit of the last patient to complete the study, or the date of receipt of the last data point from the last patient that is required for primary, secondary, and/or exploratory analysis, as pre-specified in the protocol.

End of Treatment (EOT) is defined as the date of the last dose of ABI-009 or nivolumab for an individual patient

End of Treatment Visit for a patient is when safety assessments and procedures are performed after the last treatment, which must occur at least 4 weeks (\pm 7 days) after the last dose of ABI-009 or nivolumab.

Primary analysis for this study will occur after all patients have either completed the study or completed 12 months of treatment. Patients who are still active at the time of the primary analysis may continue on study until disease progression or medication intolerance is observed.

Primary Completion is the time when the last patient is assessed or receives an intervention for the purposes of final collection of data for the primary analysis.

Follow-up period is the on-study time period after the EOT Visit. All patients that discontinue study drug and have not withdrawn full consent to participate in the study will continue in the follow-up phase for survival and anticancer therapy. Follow-up will continue approximately every 12 weeks (+/- 3 weeks), or more frequently as needed, until death, withdrawal of consent, or the study closes, whichever is the earliest. This evaluation may be made by record review and/or telephone contact.

The final patient's last visit for the study will be defined as whichever of the following represents the last time point:

- When the last patient on study has completed their Safety follow-up visit, or
- When the last patient on study has documented toxicities to ABI-009 and nivolumab, and the toxicity has resolved, returned to baseline or is deemed irreversible after the Safety follow-up visit or
- When the last patient completes or discontinues the follow-up phase

3. STUDY POPULATION

3.1. Number of Patients

The anticipated enrollment into this study will be approximately 12-18 patients for the Phase 1 part of the study and approximately 22-28 evaluable patients for the Phase 2 part of the study. The rationale for the number of patients is detailed in [Section 8](#).

The investigator will be expected to maintain a screening log of all potential study candidates that includes limited information about the potential candidate, date, and outcome of the screening process (e.g., enrolled into study, reason for ineligibility, or refused to participate).

Before any study-specific procedure, the appropriate written informed consent must be obtained (see [Section 11.5](#)).

3.2. Inclusion Criteria

A patient will be eligible for inclusion in this study only if all of the following criteria are met:

1. Patients must have a histologically confirmed diagnosis of Ewing's sarcoma, PEComa, epithelioid sarcoma, desmoid tumor, chordoma, non-small cell lung cancer, small cell lung cancer, urethelial carcinoma, melanoma, renal cell carcinoma, squamous cell carcinoma of head and neck, hepatocellular carcinoma, classical Hodgkin's lymphoma, MSI-H/dMMR metastatic colorectal cancer, and tumors with genetic mutations sensitive to mTOR inhibitors, that is either metastatic or locally advanced and for which surgery is not a recommended option.
2. Patients must have one or more measurable target lesions by CT scan or MRI. Measurable disease by RECIST v1.1, confirmed by investigator.
3. Previously treated patient with Ewing's sarcoma, PEComa, epithelioid sarcoma, desmoid tumor, chordoma, non-small cell lung cancer, small cell lung cancer, urethelial carcinoma, melanoma, renal cell carcinoma, squamous cell carcinoma of head and neck, hepatocellular carcinoma, classical Hodgkin's lymphoma, MSI-H/dMMR metastatic colorectal cancer, and tumors with genetic mutations sensitive to mTOR inhibitors, if treatment is completed after 5 half-lives or ≥ 28 days prior to enrollment, whichever is shorter.
4. Eligible patients, 12-17 years (≥ 40 kg) or 18 years old or older, with Eastern Cooperative Oncology Group (ECOG) performance status 0 or 1.
5. Patients must have the following blood chemistry levels at screening (obtained ≤ 14 days prior to enrollment (local laboratory):
 - a. total bilirubin $\leq 1.5 \times$ upper limit of normal (ULN) mg/dl

- b. AST/ALT $\leq 2.5 \times$ ULN ($\leq 5 \times$ ULN if attributable to liver metastases); alk phos $< 3 \times$ ULN (patients with alk phos > 3 ULN will be allowed if due to bone metastases) AST $\leq 2.5 \times$ ULN ($\leq 5 \times$ ULN if attributable to liver metastases)
- c. serum creatinine $\leq 1.5 \times$ ULN

6. Adequate biological parameters as demonstrated by the following blood counts at screening (obtained ≤ 14 days prior to enrollment, local laboratory):

- a. Absolute neutrophil count (ANC) $\geq 1.5 \times 10^9/L$; b. Platelet count $\geq 100,000/mm^3$ ($100 \times 10^9/L$); c. Hemoglobin ≥ 9 g/dL.

7. Serum triglyceride < 300 mg/dL; serum cholesterol < 350 mg/dL.

8. Male or non-pregnant and non-breast feeding female:
Females of child-bearing potential must agree to use effective contraception without interruption from 28 days prior to starting IP and while on study medication and have a negative serum pregnancy test (β -hCG) result at screening and agree to ongoing pregnancy testing during the course of the study, and after the end of study treatment. A second form of birth control is required even if she has had a tubal ligation.

Male patients must practice abstinence or agree to use a condom during sexual contact with a pregnant female or a female of childbearing potential while participating in the study. A second form of birth control is required even if he has undergone a successful vasectomy.

- 9. Life expectancy of > 3 months, as determined by the investigator.
- 10. Ability to understand and sign informed consent.
- 11. Willingness and ability to comply with scheduled visits, laboratory tests, and other study procedures.

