2.4. Study Duration

The study is expected to take approximately 32 months from first patient enrolled to last patient follow-up, including approximately 24 months of enrollment period, an estimated 6 months of treatment (or until treatment is no longer tolerated) and an end of treatment visit at 4 weeks (\pm 7 days) after last treatment.

The End of Study (EOS) defined as either the date of the last visit of the last patient to complete the study, or the date of receipt of the last data point from the last patient that is required for primary, secondary, and/or exploratory analysis, as pre-specified in the protocol.

End of Treatment (EOT) for a patient is defined as the date of the last dose of ABI-009 or nivolumab.

End of Treatment Visit for a patient is when safety assessments and procedures are performed after the last treatment, which must occur at least 4 weeks (\pm 7 days) after the last dose of ABI-009 or nivolumab.

Follow-up period is the on-study time period after the EOT Visit. All patients that discontinue study drug and have not withdrawn full consent to participate in the study will continue in the follow-up phase for survival and initiation anticancer therapy. Follow up will continue approximately every 12 weeks (+/- 3 weeks), until death, withdrawal of consent, or the study closes, whichever is the earliest. This evaluation may be made by record review and/or telephone contact.

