- e. Follow-up for survival and initiation of anticancer therapy can be performed by telephone contact every 12 weeks (+/- 3 weeks) or more frequently if needed, from EOT Visit. All patients that discontinue study drug and have not withdrawn full consent to participate in the study will continue in the follow-up phase for survival and anticancer therapy. This evaluation may be made by record review and/or telephone contact.
- f. Vitals and weight only.
- g. Prior: record all medications taken and procedures done \leq 28 days prior to screening; Concomitant: any medications or procedures after the signing of informed consent.
- h. For females of childbearing potential only. A serum β -hCG pregnancy test must be performed to assess patient eligibility at screening prior to first IP administration (negative results required for IP administration). Urine pregnancy test will be performed at EOT Visit (can be done locally) and as clinically indicated as per institutional guidelines.
- i. ECG to be monitored at screening, and as clinically indicated following standard of care procedures.
- j. Calculated ONLY on C1/D1; to be recalculated only if the weight changes by > 10% in subsequent cycles.
- k. Trough levels of rapamycin will be obtained immediately prior to ABI-009 infusion at Day 15 of the second and third cycles of ABI-009, a week after the first dose in both cycles.
- l. Screening CT/MRI scans must be performed within 28 days prior to study day 1, preferably as close to the day of enrollment as possible. Tumor evaluation by contrast-enhanced CT or MRI of the chest, abdomen, and pelvis will be performed during screening; every 6 weeks (\pm 3 days after C1D1 for the first year then every 12 weeks (\pm 7 days) thereafter until disease progression. EOT visit CT/MRI should be performed only for those patients that discontinue treatment for a reason other than disease progression per RECIST 1.1. If an initial observation of objective response (CR or PR) is made, a confirmation scan should be done at 6 weeks after initial observation.

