5.2.1. Day 1 Assessment

The following assessments will be performed on Day 1 of each cycle, unless otherwise specified:

- Physical examination
- Weight assessment
- BSA calculation (Calculated ONLY on C1/D1; to be recalculated only if the weight changes by > 10% in subsequent cycles)
- Concomitant medication and procedures evaluation
- Vital signs (temperature, systolic and diastolic blood pressure, and pulse)
- ECOG performance status
- Clinical chemistry panel (including but not limited to sodium, potassium, chloride, glucose, alkaline phosphatase (ALP), AST/SGOT, ALT/SGPT, serum albumin)
- CBC, differential and platelet count
- Thyroid function (every 12 weeks)
- Fasting lipids (every 12 weeks)
- Adverse Event assessment

Day 1 evaluations for Cycle 1 may be omitted if screening evaluations are performed within 72 hours of Cycle 1 Day 1. Laboratory assessments: chemistry, hematology,

coagulation, urinalysis, pregnancy test (women of child-bearing potential, includes tubal ligation)

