5.3. End of Treatment Visit Assessment

Patient participation is complete after the EOT Visit. The EOT Visit is a safety follow-up visit that is to be performed at least 4 weeks (+ 7 days) after the last dose of ABI-009 or

nivolumab. All efforts should be made to conduct this visit. If it is not possible to conduct the EOT Visit, documentation of efforts to complete the visit should be provided.

The following procedures will be completed at the EOT Visit as designated in the Schedule of Assessments ([Table 2](#)):

- Physical examination (including physical exam, ECOG Performance Status assessment, weight)
- Vital signs (eg, blood pressure, pulse, respiration rate, temperature)
- Laboratory assessments: chemistry, CBC, differential, platelet count, pregnancy test (women of child-bearing potential, includes tubal ligations)
- Imaging Assessment: CT/MRI is to be performed at the end of study visit only for those patients that discontinue treatment for a reason other than disease progression per RECIST v1.1

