9.5. Pregnancy and Breast Feeding Reporting

If a pregnancy occurs in a female patient, or female partner of a male patient, while the patient is taking protocol-required therapies, report the pregnancy to AADI as specified below. In addition to reporting any pregnancies occurring during the study, investigators should monitor for pregnancies that occur up to 3 months after the last dose of protocol-required therapies.

The investigator will follow the female patient until completion of the pregnancy, and must notify AADI Drug Safety immediately about the outcome of the pregnancy (either normal or abnormal outcome) using the Pregnancy Follow-up Report Form, or approved equivalent form. If a lactation case occurs while the female patient is taking protocol-required therapies, report the lactation case to AADI as specified below. In addition to reporting a lactation case during the study, investigators should monitor for lactation cases that occur up to 1 week after the last dose of protocol-required therapies.

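### Pregnancy tests are fixed only at screening and EOT although criterion 8 and Section 5.2.1 point to on-treatment testing, and women's contraception duty stops with study drug while Section 9.5 watches for pregnancies for 3 more months

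*Combined protocol and SAP*

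**What the plan says.** **Testing.** Criterion 8 in Section 3.2, repeated in the synopsis, requires a negative serum test at screening and that women of child-bearing potential "agree to ongoing pregnancy testing during the course of the study, and after the end of study treatment". It gives no interval. In Table 2 (Section 4) the pregnancy-test row is marked at Screening and at the EOT Visit and is blank for Days 1, 8 and 15. Footnote h adds: "Urine pregnancy test will be performed at EOT Visit (can be done locally) and as clinically indicated as per institutional guidelines". Section 5.3 also lists the EOT test. The bulleted Day 1 list in Section 5.2.1 has no pregnancy test. A fragment after the rule on omitting Cycle 1 Day 1 evaluations, however, names chemistry, hematology, "coagulation, urinalysis, pregnancy test (women of child-bearing potential, includes tubal ligation").

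**Contraception.** Under criterion 8 women "must agree to use effective contraception without interruption from 28 days prior to starting IP and while on study medication". No period after the last dose is stated. Section 9.5 says that "investigators should monitor for pregnancies that occur up to 3 months after the last dose of protocol-required therapies". Men must abstain or use a condom with a pregnant woman or "a female of childbearing potential while participating in the study". On when that ends, Section 5.3 says "Patient participation is complete after the EOT Visit", whereas Section 2.4 says "Follow-up period is the on-study time period after the EOT Visit", and Section 2.5 agrees with 2.4.

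**The concern.** Patients consent to repeated testing that the schedule never sets. A site that follows Table 2 to the letter has no scheduled test during treatment, so dosing could continue through an unsuspected pregnancy. Girls and women of child-bearing potential are eligible from age 12. The protocol already treats pregnancy as a serious matter: it requires a second contraceptive method even after tubal ligation. Section 7.7 also urges great care with hormonal contraceptives, because it is unknown whether their metabolism is affected. If the reliability of hormonal contraception is in doubt, scheduled testing is the natural backstop.

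A woman who follows criterion 8 exactly may stop contraception at her last dose, at the start of a period in which the protocol still looks for pregnancies. Men could be told to continue for about 4 weeks after the last dose or until study closure, depending on which section is read.

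**Working it through.** The plan states no figure on this point, so the check is a comparison of passages followed by calendar arithmetic.

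**Do the testing passages agree?**

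| Source | On-treatment test |
|---|---|
| Criterion 8 | Yes, at no stated interval |
| Section 5.2.1, Day 1 | Named in a fragment outside the bulleted list |
| Sections 5.2.2 and 5.2.3 | None listed |
| Table 2 grid | None |
| Footnote h | Only if clinically indicated |

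The 5.2.1 fragment also names coagulation and urinalysis, which Table 2 marks at screening only. It may be a drafting remnant, or it may list what can be skipped at Cycle 1 Day 1. Either reading implies a Day 1 test that Table 2 lacks. The EOT test satisfies the post-treatment part of criterion 8, so the testing gap is confined to the treatment period.

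**Interval between the two fixed tests.** Inputs: screening up to 14 days before Day 1 (Section 5.1, Table 2); 21-day cycles, at most 18 (Section 5.2); about 6 months of treatment expected (Section 2.4); ABI-009 on Days 8 and 15 from Cycle 2 (Section 2.3); EOT Visit 28 ± 7 days after the last dose (Section 2.5). There is no day 0 and no dose delay is assumed.

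With *n* cycles, the last ABI-009 dose falls on day 21(*n* − 1) + 15, and EOT is 28 days later. The gap is 14 + (EOT day − 1). ABI-009 infusions number 2(*n* − 1) and nivolumab infusions *n*.

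| Cycles | Last ABI-009 dose | EOT | Gap (days) | ABI-009 | Nivolumab |
|---|---|---|---|---|---|
| 8 (24 weeks) | 7×21 + 15 = day 162 | day 190 | 14 + 189 = 203 | 14 | 8 |
| 9 (27 weeks) | 8×21 + 15 = day 183 | day 211 | 14 + 210 = 224 | 16 | 9 |
| 18 (maximum) | 17×21 + 15 = day 372 | day 400 | 14 + 399 = 413 | 34 | 18 |

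The ± 7 days at EOT turns 413 into 406 to 420. A test on Day 1 of every cycle would cut the longest on-treatment gap to 21 days. The last stretch, from Cycle 18 Day 1 (17×21 + 1 = day 358) to EOT on day 400, would be 42 days.

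**After the last dose, women.** The Section 9.5 window is 3 months, about 91 days. Required contraception in that window is 0 days. The last fixed test comes at 28 days, leaving 91 − 28 = 63 days with none (91 − 35 = 56 to 91 − 21 = 70). Section 5.4 follow-up collects survival and later anticancer therapy and does not mention pregnancy. Its first nominal contact, 12 weeks after EOT, falls 28 + 84 = 112 days after the last dose, when the window has closed.

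**After the last dose, men.** The requirement lasts about 28 days if participation ends at the EOT Visit (Section 5.3), or until the study closes if follow-up counts as on-study (Sections 2.4 and 2.5).

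**The case against.** Criterion 8 asks only for agreement to testing and sets no frequency, and footnote h permits tests when indicated. A site can comply with both, so this is an unspecified interval more than a contradiction. The 5.2.1 fragment is weak evidence of intent. Section 9.5 is a monitoring and reporting window, and nothing in the protocol says that contraception must match it. On either reading, men are covered past the last dose. The consent form is not in the reviewed copy and may set a post-dose period. The 413-day figure needs all 18 cycles, which is optimistic in previously treated advanced cancer, and it counts only fixed tests. A 12-weekly test, matching thyroid function and lipids, would also count as ongoing.

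Much of this stands. The contraception point is a misalignment and not a strict conflict. The 6-month figures describe the expected patient better than the 18-cycle ones. In the other direction, permitted dose holds would lengthen every interval shown. None of this removes the core problem: the schedule as written contains no on-treatment test, and the women's rule as written ends at the last dose. A consent form might mitigate this but would not reconcile the protocol's own sections.

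**Conclusion.** The concern holds. Fixed tests are about 203 to 224 days apart at the expected treatment length and 413 days apart (406 to 420) at the maximum. About 91 days after the last dose carry no stated contraception duty for women, and about 63 of them (56 to 70) follow the last fixed test. The men's end point has two readings.

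The figures assume screening 14 days before Day 1, no dose delays and no discretionary tests. The documents do not say how many of the planned 40 to 50 patients will be women of child-bearing potential, so the number exposed cannot be estimated. The MTD, DCR and other analyses are untouched. The change should be made because the rules, followed exactly, protect patients less than the protocol evidently intends, and the remedy is cheap.

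**What to change.** - **Table 2 and footnote h:** add a urine pregnancy test on Day 1 of each cycle for women of child-bearing potential. Move the test into the Section 5.2.1 bulleted list, and remove or correct the trailing fragment there.
- **Criterion 8 (Section 3.2 and synopsis):** require contraception in both sexes until at least 3 months after the last dose of either drug, matching Section 9.5. Use a longer period if the product information to which the protocol refers requires it; that text is not in the documents and needs checking.
- **Men:** replace the participation-based end point with the same fixed time after the last dose.

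**Cost:** wording changes, a matching consent update, and up to 18 urine tests per woman over the full course (8 to 9 at 6 months), all at Day 1 visits that already take place. Patients take on about 3 more months of contraception after the last dose.

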3.3. Exclusion Criteria

A patient will not be eligible for inclusion in this study if any of the following criteria apply:

- 1. Known active uncontrolled or symptomatic central nervous system (CNS) metastases. A patient with controlled and asymptomatic CNS metastases may participate in this study. As such, the patient must have completed any prior treatment for CNS metastases ≥ 28 days (including radiotherapy and/or surgery) prior to start of treatment in this study and should not be receiving chronic corticosteroid therapy for the CNS metastases.
- 2. Active gastrointestinal bleeding.
- 3. Pre-existing thyroid abnormality is allowed provided thyroid function can be controlled with medication.
- 4. Uncontrolled serious medical or psychiatric illness. Patients with a “currently active” second malignancy other than non-melanoma skin cancers, carcinoma in situ of the cervix, resected incidental prostate cancer (staged pT2 with Gleason

Score ≤ 6 and postoperative PSA <0.5 ng/mL), or other adequately treated carcinoma-in-situ are ineligible. Patients are not considered to have a “currently active” malignancy if they have completed therapy and are free of disease for ≥1 year).

5. Liver-directed therapy within 2 months of enrollment. Prior treatment with radiotherapy (including radio-labeled spheres and/or cyberknife, hepatic arterial embolization (with or without chemotherapy) or cyrotherapy/ablation) is allowed if these therapies did not affect the areas of measurable disease being used for this protocol.
6. Recent infection requiring systemic anti-infective treatment that was completed ≤14 days prior to enrollment (with the exception of uncomplicated urinary tract infection or upper respiratory tract infection).
7. Uncontrolled diabetes mellitus as defined by HbA1c >8% despite adequate therapy.
8. Unstable coronary artery disease or myocardial infarction during preceding 6 months.
9. Receiving any concomitant antitumor therapy.
10. Patients with history of interstitial lung disease and/or pneumonitis, or pulmonary hypertension.
11. Use of strong inhibitors and inducers of CYP3A4 within the 14 days prior to receiving the first dose of ABI-009. Additionally, use of any known CYP3A4 substrates with narrow therapeutic window (such as fentanyl, alfentanil, astemizole, cisapride, dihydroergotamine, pimozide, quinidine, terfanide) within the 14 days prior to receiving the first dose of ABI-009.
12. Known Human Immunodeficiency Virus (HIV).
13. Active Hepatitis B or Hepatitis C.
14. Non-oncology vaccine therapy used for prevention of infectious disease within 4 weeks of trial enrollment
15. Autoimmune disease including rheumatoid arthritis, systemic progressive sclerosis (scleroderma), systemic lupus erythematosus, autoimmune vasculitis and motor neuropathy considered to be of autoimmune origin (e.g. Guillain-Barre Syndrome)
16. Systemic immunosuppression, including HIV positive status with or without AIDS
17. Skin rash (psoriasis, eczema) affecting > 25% body surface area
18. Inflammatory bowel disease (Crohn's or ulcerative colitis)
19. Ongoing or uncontrolled diarrhea within 4 weeks of trial enrollment
20. Recent history of acute diverticulitis, intraabdominal abscess or gastrointestinal obstruction within 6 months of trial enrollment, which are known risk factors for bowel perforation
21. Current, active or previous history of heavy alcohol abuse
22. Pituitary endocrinopathy and Adrenal insufficiency or excess

